8.1 Statistical design

8.1.1 Sample size

Groups A and B

This is an open label, non-randomized, multi-center trial using the classical 3+3 design.

In both groups A and B, a minimum of 3 patients will be included at each dose level. There is no intention to increase the dose of TG02 above 150 mg in Groups A and B. Within one dose level, patients may be entered simultaneously. The second dose level may be started when all patients of dose level 1 have completed cycle 1 (28 days).

In case of occurrence of 1 DLT, an additional 3 patients will be added in order to ensure the safety profile of this dose level unless a DLT is documented immediately in any additional patient entered at this dose level. If 2 DLT are observed in the first 3 patients dose escalation will stop without need to extend the dose level to 6 patients.

The replacement of patients will be performed in case of patients that progress, die due to disease progression, or leave study for any reason other than DLT prior to completion of the first cycle of therapy.

After determination of the MTD, additional patients will be treated at the highest dose level for additional safety information in the absence of safety issues up to a total of 24 evaluable patients in Group A and up to a total of 12 evaluable patients in Group B (up to 36 evaluable patients for Groups A and B). We consider groups A and B exploratory and independent from each other, with the prime goal of assessing feasibility (tolerability, safety). The difference in size in these two groups reflects the natural distribution of patients into those with tumors without (2/3, group A) and with (1/3, group B) MGMT promoter methylation. The elderly patient population is ideally suited to explore safety, tolerability and efficacy of TG02 with the two backbones of glioblastoma treatment, radiotherapy (group A) and temozolomide (group B), in isolation. Finally, there is a feasibility consideration: we anticipate that doctors and patients are more willing to omit temozolomide in group A than to omit radiotherapy in arm B although such a strategy is consistent with the EANO guideline updated in 2017 (Ref. 35).

Number of Patients with DLT at a Dose Level	Dose Escalation Decision Rule in Groups A and B
0 out of 3	Enroll 3 patients at the next dose level up to a maximum TG02 dose of 150 mg.
≥ 2 out of 3 or 6	
Dose escalation is stopped. If it occurs at 100 mg then trial is stopped without MTD. If it occurs at 150 mg then 100 mg is considered the MTD and as the recommended dose for phase II.
 
The safety at the MTD will also be assessed in additional patients up to a maximum of 24 patients in group A and 12 patients in group B. These totals include all patients recruited in the 3+3 escalation phase.

1 out of 3	
Enroll at least 3 more patients at this dose level.
 
If 0 of these 3 patients experience DLT, proceed to the next dose level up to a maximum TG02 dose of 150 mg. If it occurs at 150 mg then 150 mg is considered the MTD and as the recommended dose for phase II.
 
If 1 or more of this Group experience DLT, then dose escalation is stopped. If it occurs at 100 mg then trial is stopped without MTD. If it occurs at 150 mg then 100 mg is considered the MTD and as the recommended dose for phase II.
 
The safety at the MTD will also be assessed in additional patients up to a maximum of 24 patients in group A and 12 patients in group B. These totals include all patients recruited in the 3+3 escalation phase.

DLT = dose limiting toxicity

MTD = maximum tolerated dose

The MTD corresponds to the highest dose at which not more than 1 patient out of a maximum of 6 experiences a DLT. A compliance of 75% for TG02 and either RT (Group A) or TMZ (Group B) is required to assess the toxicity.

Group C

Further to the IDMC recommendations, the initial dose of TG02 was reduced from 200 to 150 mg with potential to escalate to 200 mg in case the first full cycle was well tolerated. During the follow-up IDMC meeting, the IDMC recommended to stop escalation to 200 mg. The initial statistical design remains applicable to eligible patients treated at initial dose of 150 mg.

Data collected at initial dose 200 mg (n=18) and 250 mg (n=6) will be analyzed for descriptive purpose only i.e., will not be included in the analysis below (primary analysis.)

Based on an A'Hern one-stage design, 45 eligible patients who started treatment will be evaluated for PFS at 6 months. It is estimated that the total sample size should not be larger than 50 assuming a dropout of 10%.

The following hypotheses apply:

- P_0 is the largest PFS rate at 6 months which, if true, implies that the therapeutic activity of TG02 is too low. In the present trial, P_0 has been taken as 20%.
- P_1 is the lowest PFS rate at 6 months which, if true, implies that the therapeutic activity of TG02 is adequate. In the present trial, P_1 has been taken as 40%.

- α is the probability of accepting adequate activity of TG02 with a true PFS rate at 6 months equal to or lower than P_0 . In the present trial, α has been taken as 0.10.
- β is the probability of rejecting adequate activity of a drug with a true PFS rate at 6 months at least equal to P_1 . In the present trial, β has been taken as 0.05.

A decision rule for efficacy will be performed amongst the 45 patients:

- If < 13 patients are free of progression and alive at 6 months, the conclusion will be that TG02 should not be further investigated.
- If ≥ 13 patients free of progression and alive at 6 months are observed, we will conclude that TG02 should be further investigated. In this case, the one-sided 90% confidence interval excludes P_0 .

8.1.2 Randomization and stratifications

No randomization or stratification will be used in this study.

8.2 Statistical analysis plan

Each of the three groups will have a separate final analysis report. These reports and related publications can be released at different time points.

8.2.1 Analysis populations

- Intention-to-treat population: All enrolled patients will be analyzed in the arm they were allocated by.
- Efficacy population: All patients who are eligible and have started their allocated treatment (at least one dose of TG02).
- Safety population: All patients who have started their allocated treatment (at least one dose of TG02 and were not replaced in phase Ib).

A patient will be considered to be eligible if he/she did not have any deviation from the patient entry criteria listed in chapter 3 of the protocol. Potential eligibility problems will be assessed by the Clinical Research Physician of the EORTC Brain Tumor Group at time of medical review.

8.2.2 Statistical methods

Group A and B

Primary endpoints are the determination of the Maximum Tolerated Dose (MTD) and the recommended phase II combination dose. All analyses will be performed in the safety population. Analyses will be descriptive only presented with tables and listings (i.e. no formal inference). Objective response rate will be reported with exact (binomial) 95% two-sided confidence interval. The PFS-6 and OS-9 and the medians will be extracted from their Kaplan-Meyer curves. The 95% two-sided confidence intervals will be computed based on the Greenwood's formula and based on the Reflected Method for the median. The best overall response will be presented in contingency table with numbers and percentages. The objective response (CR+PR) and complete response (CR) rates will be reported with exact (binomial) 95% two-sided confidence interval. Duration of objective response and complete response will be estimated using Kaplan-Meier methodology. Median duration of objective and complete response with corresponding 95% two-sided confidence interval provided by the Reflected Method will be displayed. Hematological and biochemistry parameters will be presented with clinical significance (CS vs NCS).

Safety and efficacy data in patients excluded from the safety population will be reported separately.

Group C

- Number of patients free of progression at 6 months (primary analysis)

In the efficacy population:

All patients will be observed during a minimum follow-up of 6 months. The number of patients free of progression and alive at 6 months will be computed and the above-mentioned decision rule applied. Patients lost to follow-up or who died before 6 months are considered as failures at the time of analysis. In case more than 45 eligible patients are recruited, the decision rule will be applied as such on the first 45 eligible patients. The proportion of patients free of progression at 6 months will be presented with 80% two-sided confidence intervals computed based on the Exact Binomial distribution.

- Progression free survival

In the efficacy population:

The primary endpoint, PFS rate at 6 months (PFS6) and the median PFS will be extracted from the Kaplan-Meyer PFS curve. For PFS6, 80% two-sided confidence intervals and 95% two-sided confidence intervals will be computed based on the Greenwood's formula. For the median the Reflected Method will provide 95% two-sided confidence intervals.

These estimates will be presented both based on investigator and centrally reviewed progression data.

- Overall survival

In the efficacy population:

The OS rate at 9 months (OS-9), 1 year (OS-12) and the median will be extracted from the Kaplan-Meyer OS curve. For OS-9 and OS-12 95% two-sided confidence intervals will be computed based on Greenwood's formula. For the median the Reflected Method will provide 95% two-sided confidence intervals.

- Response and duration of response

In the efficacy population:

The best overall response will be presented in contingency table with numbers and percentages. The objective response (CR+PR) and complete response (CR) rates will be reported with exact (binomial) 95% two-sided confidence interval.

Duration of objective response and complete response will be estimated using Kaplan-Meier methodology. Median duration of objective and complete response with corresponding 95% two-sided confidence interval provided by the Reflected Method will be displayed.

These estimates will be presented both based on investigator and centrally reviewed response data.

- Success rate

In the efficacy population:

The success rate will be reported with exact (binomial) 95% two-sided confidence interval.

Success rate will be presented both based on investigator and centrally reviewed response data.

- Neurologic progression free survival

In the efficacy population:

The NPFS rate at 6 months (NPFS6) and the median NPFS will be extracted from the Kaplan-Meyer PFS curve. For NPFS6, 95% two-sided confidence intervals will be computed based on the Greenwood's formula. For the median the Reflected Method will provide 95% two-sided confidence intervals.

- Comparison of PFS by local investigator and by central review and comparison of NPFS and CDFS.

In the efficacy population:

The differences of times to event between these estimates will be tabulated.

- Safety and tolerability

In the safety population:

The safety and tolerability analyses will be presented at baseline and up to 30 days after the last administration of study drug. Baseline will include all information recorded up to the nearest date prior to or at randomization. Exceptionally in absence of this assessment, the first assessment performed after randomization but before start of protocol treatment can be considered as baseline.

Baseline laboratory and AE grades will not be accounted for in whole treatment safety analyses.

Laboratory events of clinical significance (CS) will be reported on the adverse events CRFs and will be reported separately.

- Hematological parameters

The worst value of each hematological category will be identified and graded for each patient.

Frequencies and percentages of each category will be tabulated. A table with grade 3/4 frequencies and percentages will also be displayed. The frequencies and percentages of patients with at least one grade 1 or one grade 3 or 4 hematological toxicity will be presented.

- Biochemistry parameters

The worst value of each biochemical category will be identified and graded for each patient. Frequencies and percentages of each category will be tabulated. A table with grade 3/4 frequencies and percentages will be displayed. The frequencies and percentages of patients with at least one grade 1 or one grade 3 or 4 biochemistry toxicity will be presented.

- All adverse events

The worst grade of each AE item will be identified for each patient. Frequencies and percentages of each category will be tabulated. Tables with all grades, grades 3 or 4 and grades 5 frequencies and percentages will be displayed. The frequencies and percentages of patients with at least one grade 1 or one grade 3 or 4 or one grade 5 AE will be presented.

- Related AEs

The worst grade of each likely related AE item will be identified for each patient. Frequencies and percentages of each related AE category will be tabulated. Tables with related grades, grades 3 or 4 and grade 5 frequencies and percentages will be displayed. The frequencies and percentages of patients with at least one related grade 1 or one related grade 3 or 4 or one related grade 5 AE will be presented.

- SAEs and Related SAEs

After reconciliation with the SAEs listing extracted from the EORTC pharmacovigilance database, the worst grade of each (related) serious AE category will be identified for each patient. Frequencies and percentages of each category will be tabulated. Tables with all (related) grades, (related) grades 3 or 4 and (related) grades 5 frequencies and percentages will be displayed. The frequencies and percentages of patients with at least one (related) grade 1 or one (related) grade 3 or 4 or one (related) grade 5 SAE will be presented.

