6.3.3 Follow-up every 3 months (\pm 14 days)

For all groups:

- Survival, irrespective of type of treatment administered or any progression event. (Follow-up can be done by regular visits or phone calls.)
- If progression has not occurred,
 - Brain Gd-MRI (Appendix J)
 - Quality of life assessment (modified EORTC QLQ C30/BN20) Group A & B only

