7.2.2 Efficacy

To ensure a homogeneous radiological evaluation, all MRI images will be retrospectively centrally reviewed.

The following criteria will be used to determine the efficacy of study treatment.

Progression Free Survival (PFS): PFS is defined as the number of days from consent to the date of earliest disease progression based on Response Assessment in Neuro Oncology (RANO) criteria (as determined by the Investigator) or to the date of death, if disease progression does not occur. In group C, patients for whom neither death nor progression have been documented will be censored on the date of the last radiological assessment if they have no post anti-cancer therapy. If a patient has other post anti-cancer therapy prior to progression or death, the data will be censored at the date of last radiological assessment prior to or on the start date of post anti-cancer therapy. In group A and B, post anti-cancer therapy is not collected. The data will be censored at the date of the last radiological assessment. In all groups, if a patient with no post-baseline radiological assessment did not experience progression nor died, then the data will be censored at the date of enrollment.

PFS at 6 months (PFS-6) is the PFS rate at 6 months extracted from the PFS Kaplan Meier distribution based on RANO criteria (as determined by the Investigator)

Overall Survival (OS): OS is defined as the number of days from consent to the date of death due to any cause. If a patient has not died, the data will be censored at the last date documented to be alive.

OS at 9 months (OS-9) is the OS rate at 9 months extracted from the OS Kaplan Meier distribution.

Objective (ORR) and complete (CR) response rates are the proportions of patients with best overall response PR+CR or CR (see below) respectively.

Duration of objective (complete) response (DOR): DOR is determined as the number of days from the time point where the overall response PR or CR (CR) was first seen to the earliest date of detection of disease progression based on RANO criteria (as determined by the Investigator) or to the date of death, if disease progression does not occur. The same censoring rules defined above for PFS are applicable.

A success is defined as a patient achieving either confirmed CR or PR (> 4 week) or free of progression at 6 months.

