4. For patients receiving antiangiogenic therapy, significant increase in T2/FLAIR nonenhancing lesion may also be considered progressive disease. The increased T2/FLAIR must have occurred with the patient on stable or increasing doses of corticosteroids compared with baseline scan or best response after initiation of therapy and not be a result of comorbid events (e.g., effects of radiation therapy, demyelination, ischemic injury, infection, seizures, postoperative changes, or other treatment effects).

If the evidence of PD is equivocal (target or non-target lesions), treatment may continue until the next assessment, but if PD is confirmed at the next follow-up, the earlier date must be used as the date of progression.

In case non-measurable tumor is left after surgery i.e. tumor less than 10x10 mm, unequivocal progression of non-target lesion may be accepted as evidence of disease progression, where the overall tumor burden has increased sufficiently to merit discontinuation of treatment. Modest increase in the size of a non-target lesion is NOT considered unequivocal progression. If the evidence of PD is equivocal (target or non-target), treatment may continue until the next assessment, but if confirmed, the earlier date must be used as the date of progression. This implies that in case of gross total resection of the

enhancing lesion, if at follow up minimal enhancement of unclear significance arises, treatment may continue until further follow-up gives unequivocal evidence of tumor progression.

Stable Disease (SD):

This occurs if the patients did not qualify for complete response, partial response, or progression (see above) and requires: 1) No meaningful change in the appearance of the FLAIR/T2 images compared to baseline or to the nadir (point with the smallest FLAIR/T2 abnormalities) if a decrease occurred.

Evaluation of response, treatment decision and central review:

- For this trial, the primary measure of response and progression will be determined by the locally assessed response according to the RANO criteria. The time point of progression will be determined at the sites, although the centers in Zurich and Vienna (Reference Neuroradiology) will be happy to provide support.
- Study treatment is completed at the time of first progression. Follow-up until death or the end of data acquisition is required within this trial.

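### Group C's centrally reviewed PFS-6, PFS and DOR have no event and censoring rule of their own; under the investigator rule, many site-only progressions would be censored, probably biasing the central estimates upward

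*Combined protocol and SAP*

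**What the plan says.** Four parts of the combined protocol and SAP bear on this.

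- **Estimator (8.2.2, Group C).** PFS-6 and median PFS are read from a Kaplan-Meier curve, and DOR is also Kaplan-Meier. On PFS the section adds: "These estimates will be presented both based on investigator and centrally reviewed progression data". A parallel sentence covers response and DOR. For PFS by site, PFS by central review, NPFS and CDFS, it says: "The differences of times to event between these estimates will be tabulated".
- **Event and censoring rules (7.2.2).** Progression is the investigator's. "In group C, patients for whom neither death nor progression have been documented will be censored on the date of the last radiological assessment", provided no other anti-cancer therapy was given. If such therapy came first, censoring is at the last scan on or before its start. Death without recorded progression is an event. DOR uses the same rules. No separate rule is given for central data.
- **What ends scanning.** Section 7.2.5 says: "Study treatment is completed at the time of first progression", and progression is called at the site. In 6.3.3 the three-monthly MRI carries the condition "If progression has not occurred". The post-progression list in 6.3.3.1 contains survival and later therapy for Group C, but no MRI.
- **Central review.** Section 16.5.1.4 makes it retrospective and leaves further detail to a separate Central Review Charter. Section 7.2.5 calls it a secondary analysis.

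The only PFS sensitivity analysis in 8.2.3 for Group C repeats the analysis in the intention-to-treat population.

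**The concern.** Central review is meant to check the site's reading, but the site's call decides how much imaging the central reader sees. Take a patient called progressive by the site and not by the central reader. Treatment stops and the scheduled scans end. If new therapy starts, 7.2.2 censors the central PFS at the last scan before it, which will often be the scan on which the site saw progression. Kaplan-Meier then assumes that this patient has the same later risk as patients both readers consider stable, which is hard to believe.

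Some disagreement may be built in. Under 7.2.3 and 7.2.5 the site can declare progression on clinical deterioration, whereas 16.5.1.4 describes the central review as a review of scans.

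Group C is single-arm and open-label, with a locally read primary endpoint. A central PFS-6 that is too high would give false reassurance about the local reading. It would also not be like-for-like with the primary count, which treats loss to follow-up as failure.

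**Working it through.** **The plan's own figure.** Section 8.1.1 states that P0 "has been taken as 20" percent, P1 "has been taken as 40" percent and alpha "has been taken as 0.10", with beta 0.05, 45 patients and a go decision at 13 or more. The exact binomial gives P(X ≥ 13 | n = 45, p = 0.20) = 0.0995 and P(X ≥ 13 | n = 45, p = 0.40) = 0.955. A search over n = 30 to 51 finds 45 to be the smallest n meeting both limits, and 45/0.9 = 50. The one-sided 90% lower limit at 13/45 is 0.2002, just above P0. The design reproduces.

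**Size of the bias.** The documents give no figure for central PFS-6, so what follows is an illustration. Scans are at about days 56, 112 and 168 (every two cycles to cycle 6). Assumptions:

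- S: local PFS-6, set at 20% or 40%, with equal hazard per scan, q = 1 − S^(1/3). This gives q = 0.415 or 0.263.
- f: share of site progressions not confirmed centrally, 10 to 30%.
- d: share of those patients who die without new therapy before the next assessment (events), 0 or 30%. The rest are censored at the scan.
- h: chance per later scan that an unconfirmed patient would be called centrally had scanning continued, 0.75 or 1.

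Central Kaplan-Meier PFS-6 = [(1 − q(1−f)) × (1−q) / ((1−q) + d·q·f)]³. With d = 0 this is (1 − q(1−f))³.

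Central PFS-6 with continued scanning = S + q·f·(1−d) × [(1−h)² + (1−q)(1−h) + (1−q)²].

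Example with S = 20%, f = 20%, d = 0: Kaplan-Meier = (1 − 0.415 × 0.8)³ = 29.8%. Continued scanning with h = 0.75 gives 0.20 + 0.083 × (0.0625 + 0.146 + 0.342) = 24.6%. The bias is 5.2 points.

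| Local PFS-6 | f | d | Kaplan-Meier | Continued, h = 0.75 | Continued, h = 1 | Bias (points) |
|---|---|---|---|---|---|---|
| 20% | 10% | 0 | 24.6% | 22.3% | 21.4% | 2.3–3.2 |
| 20% | 20% | 0 | 29.8% | 24.6% | 22.8% | 5.2–7.0 |
| 20% | 30% | 0 | 35.7% | 26.9% | 24.3% | 8.8–11.4 |
| 20% | 10% | 30% | 23.1% | 21.6% | 21.0% | 1.5–2.1 |
| 20% | 20% | 30% | 26.3% | 23.2% | 22.0% | 3.1–4.3 |
| 20% | 30% | 30% | 29.6% | 24.8% | 23.0% | 4.8–6.6 |
| 40% | 10% | 0 | 44.4% | 42.1% | 41.4% | 2.3–3.0 |
| 40% | 20% | 0 | 49.2% | 44.2% | 42.9% | 5.0–6.3 |
| 40% | 30% | 0 | 54.3% | 46.2% | 44.3% | 8.1–10.0 |
| 40% | 10% | 30% | 43.0% | 41.5% | 41.0% | 1.5–2.0 |
| 40% | 20% | 30% | 46.2% | 42.9% | 42.0% | 3.3–4.2 |
| 40% | 30% | 30% | 49.4% | 44.4% | 43.0% | 5.0–6.4 |

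**Equal later risk.** Set h = q(1−f), the central hazard of those still followed. With d = 0 the two estimates coincide and the bias is zero. With d = 30% the Kaplan-Meier value falls 0.1 to 1.4 points below.

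**Site call counted as an event.** In this model the estimate returns to 20% or 40%, which lies below the continued-scanning value.

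**The case against.** The case on the other side is substantial.

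- **Not every unconfirmed patient is censored at that scan.** A reader might infer this, but the documents do not support it. Death without prior new therapy is an event (7.2.2). Section 6.3.1 requires an MRI at the end-of-study visit, within 30 days (±5) of the last dose. For unclear progression, 7.1.8 recommends continued treatment and a new MRI, and 7.2.5 lets treatment run to the next assessment. These reduce the problem without removing it, because 7.2.2 excludes scans after new therapy starts.
- **The central use of the 7.2.2 rule is inferred.** That section defines progression by the investigator, and the Charter is not among the documents. This stands. Either 7.2.2 governs and the bias follows, or the protocol leaves the rule unstated. Both call for a sentence in 8.2.2.
- **The gap between central and local PFS-6 is not all bias.** Reading 20% against 24.6 to 35.7% mixes real reader disagreement with censoring, so the table compares with continued scanning. Disagreement can also run the other way. With S = 20% and f = 20%, central calls in q·f/(1−q) = 0.083/0.585 = 14% of locally stable patients per scan would bring the central figure back to 20%. That changes the level and leaves the censoring mechanism in place.
- **No decision turns on it.** It is tempting to set an inflated central figure beside 13/45 = 28.9% and say that an inactive drug could pass. The plan never applies that rule to the central curve. The primary count is local and uncensored, with loss and death as failures.
- **The time-difference table.** Section 8.2.2 does not say that censored times are subtracted as events. It is silent on how they are handled.
- **Using the site's call as a central event weakens the independent check.** This is fair, and it is why that version belongs in a sensitivity analysis.

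**Conclusion.** The point holds as a gap with a probable direction. The central PFS-6, median PFS and DOR have no event and censoring rule of their own. The only rule available would censor many site-only progressions at or near the site's call, chiefly in patients who start new therapy.

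If unconfirmed patients are at higher later risk than those still followed, central PFS-6 is too high by about 1.5 to 11 points. That range rests on assumed discordance of 10 to 30%, equal hazard per scan, and a chance of 0.75 to 1 per later scan of central progression. No size was computed for median PFS or DOR, where the mechanism is the same.

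Upward bias is likely rather than certain, and it is measured against central reading with full scanning. The central figure could still fall below the local one. The go/no-go decision stands as designed. What is at risk is the reading of a secondary but important check on an open-label, single-arm result.

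**What to change.** 1. In 8.2.2, state the event and censoring rule for central PFS-6, PFS and DOR, including what happens to a patient with site progression and no later centrally readable scan.
2. In 8.2.3, prespecify a sensitivity analysis of the same three estimates in which site progression without such a scan, or the start of new therapy, is an event at that date. Show it beside the censored version. The two act as bounds provided that unconfirmed patients are at no lower later risk than those still followed.
3. Report a site-by-central agreement table with the number of site-only progressions, so that the assumed discordance is replaced by the observed one.
4. Limit the table of time differences to patients with an event by both methods, and give the number left out.

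The cost is SAP wording and a few tables, with no new data collection. The event version borrows the site's call, so it should be labelled a conservative bound and should not become the headline central estimate. The wording should be settled before central results are seen.
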